4.5. CLINICAL PHARMACOLOGY DATA ANALYSES

4.5.1. Pharmacokinetic Analyses

In this study, GSK3511294 plasma concentration are collected at discrete timepoints during the 52-week treatment period. GSK3511294 plasma concentration will be summarised by visit. (GSK3511294 + SoC arm only).

The PK data from this study will be included in a meta-analysis of the PK and PKPD data across all GSK3511294 studies. Details of meta-analysis will be in a separate CPMS analysis plan.

4.5.2. Pharmacodynamic Analyses - Blood Eosinophils

Blood eosinophil counts will be loge-transformed prior to analysis. Non-detectable blood eosinophil values of 0 GI/L, or results below the limit of quantification will be imputed with a value of 0.005GI/L prior to log transformation.

Ratio to baseline during W52 will be analysed using a MMRM analysis. Model specification, model checking and diagnostics are the same as described for secondary endpoints statistical analyses, see Section 4.3.1. Analysis will include data from all visits that blood eosinophils data is collected. LS Mean (SE) and LS Mean ratio to screening (SE) in each treatment group will be presented. Mean treatment ratio and 95% CI for GSK3511294 vs placebo will also be presented.

Absolute and ratio to baseline blood eosinophil counts will be summarised by treatment group and visit. Only results from the central laboratory will be included in the summary.

4.6. Safety Analyses

All safety analyses will be performed on the Safety Analysis Set unless otherwise specified. Summaries of data will report data according to the nominal visit for which it was recorded. Occurrence of Adverse Events (AEs), Serious Adverse Events (SAEs), Adverse Events of Special Interest (AESIs), laboratory data, vital signs, and ECGs will be included in data displays in the form of frequency tables, summary statistics, graphs, and statistical analyses where appropriate.

4.6.1. Extent of Exposure

Two doses of study treatment will be administered during study treatment period: the first at randomisation Visit 2 (Week 0) and the second at Visit 10 (Week 26). Each dose is viewed as providing therapeutic coverage for 26 weeks (182 days). The number of treatments administered and the number of days exposure will be summarised descriptively and listed. Total subject-year exposure will also be presented.

Number of days of exposure to study treatment will be calculated as follow:

Duration of Exposure in Days = (Date of Final Dose) – (Date of First Dose) + 182

Subject years exposure is calculated as follow:

Subject Years Exposure = ((Date of Final Dose) – (Date of First Dose) + 182)/365.25

The exposure summary will also be presented by age subgroup $(12-17, 18-64, \ge 65)$.

4.6.2. Adverse Events

Adverse events analyses including the analysis of adverse events (AEs), Serious AEs (SAEs) and other significant AEs will be based on GSK Core Data Standards.

An overview summary of AEs, including counts and percentages of participants with any AE, AEs related to study intervention, AEs leading to permanent discontinuation of study intervention or withdrawal from study, study intervention related AEs leading to

permanent discontinuation of study intervention or withdrawal from study, SAEs, SAEs related to study intervention, fatal SAEs, and fatal SAEs related to study intervention will be produced. These summaries will also be produced by age subgroup (12-17, 18-64, ≥ 65).

Adverse events will be coded using the standard Medical Dictionary for Regulatory Affairs (MedDRA dictionary).

The frequency and percentage of AEs will be summarised in two ways: 1) in descending order by System Organ Class (SOC) and Preferred Term (PT), where exposure-adjusted incidence rate will also be summarised. 2) in descending order by PT only.

Common (>=3%) on treatment AEs will be summarised by overall frequency and summarised by time to onset.

A separate summary will be provided for study intervention-related AEs. A study intervention-related AE is defined as an AE for which the investigator classifies the possible relationship to study intervention as "Yes". A worst-case scenario approach will be taken to handle missing relatedness data, i.e. the summary table will include events with the relationship to study intervention as 'Yes' or missing. The summary table will be displayed in descending order by SOC and PT.

AE will also be summarised by subgroups of age 1, age 2, age 3, gender, race and region by SOC and PT.

All SAEs will be tabulated based on the number and percentage of participants who experienced the event. Separate summaries will also be provided for study intervention-related SAEs. The summary tables will be displayed in descending order by SOC and PT.

A study intervention-related SAE is defined as an SAE for which the investigator classifies the relationship to study intervention as "Yes". A worst-case scenario approach will be taken to handle missing data, i.e. the summary table will include events with the relationship to study intervention as 'Yes' or missing. The summary table will be displayed in descending order by SOC and PT.

4.6.2.1. Adverse Events of Special Interest

Adverse events of special interest (AESI) for GSK3511294 program include:

• Allergic (Type 1 hypersensitivity) reactions including anaphylaxis

Note: these events will be assessed by the investigator as to whether they meet the diagnostic criteria for anaphylaxis as outlined by the 2006 Joint NIAID/FAAN Second Symposium on Anaphylaxis.

- Type III hypersensitivity (immune complex disease/vasculitis) reactions
- Local injection site reactions
- QTc prolongation

AESI reported by the investigator as systemic reactions (further categorised by the investigator as either allergic [type I hypersensitivity] or other systemic reactions and assessed against Sampson criteria for anaphylaxis) are collected via targeted eCRF within the study. Vasculitis events and local injection site reactions are also collected via targeted eCRF within the study.

Separate summary tables showing the number and percent of subjects with each type of AESI (excluding QTc prolongation) broken down by preferred term will be created.

For each type of AESI (excluding QTc prolongation) a profile summary table will be produced containing information including, but not limited to, the number of occurrences of the event, event characteristics, time to onset, intensity, outcome and action taken.

A summary of the incidence of serious adverse events and adverse events of special interest (excluding QTc prolongation) will be produced displaying the relative risk and risk difference and their 95% CIs between and GSK3511294 and placebo.

AESI of QTc prolongation will be summarised as detailed in Section 4.6.3.3 ECG.

4.6.3. Additional Safety Assessments

4.6.3.1. Laboratory Data

Summaries of laboratory data including chemistry and haematology parameters, and liver chemistry test data will be based on GSK Core Data Standards and unless otherwise specified will include on-treatment and post-treatment data.

A scatter plot of maximum post-baseline ALT vs maximum post-baseline total bilirubin will be produced. In addition, if any liver stopping or liver monitoring events occur during the study, summaries of liver monitoring/stopping event reporting and hepatobiliary laboratory abnormalities will be produced.

Samples for anti-MPO antibody, anti-PR3 antibody, ANA, and antidsDNA antibody are collected at baseline visit and if clinically indicated post baseline, analysed on as needed basis and will be summarised only for participants with data available.

The details of the planned displays will be in OPS.

4.6.3.2. Vital Signs

Pre-dose systolic blood pressure, diastolic blood pressure, pulse rate and body temperature including change from baseline at all visits will be summarised.

4.6.3.3. ECG

Change from baseline (for post-baseline timepoints) values for QTc(F), and heart rate will be summarised by treatment for Baseline, Week 2, Week 26, Week 28, and Week 52. ECG findings will be summariesd by visit.

Individual maximum QTc(F) values will also be summarised to show the number of subjects with maximum values (msec) post-baseline relative to baseline in the following

categories: Decrease, no change or increase to ≤ 450 , increase to $450 < to \leq 480$, increase to $480 < to \leq 500$, increase to $500 < to \leq 530$ and increase to > 530. QT uncorrected values will be summarised to show the number of subjects with maximum values (msec) post-baseline relative to baseline in the following categories: Decrease, no change or increase to ≤ 600 and increase to ≥ 600 .

Additionally, individual maximum changes from baseline in QTc(F) values will be summarised to show the number of subjects with maximum changes (msec) in the categories: increase of ≤ 30 , increase of 31 to 60 and increase of ≥ 60 .

All ECG values for participants with protocol defined QT stopping criteria will be listed.

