7.1.2. QTc Stopping Criteria

Details on performing ECG assessments can be found in [Section 8.3.3](#).

The QT interval corrected using Fridericia’s formula (QTcF) must be used for *each individual participant* to determine eligibility for and discontinuation from the study intervention. This formula may not be changed or substituted once the participant has been enrolled.

For this study, the following QTc stopping criteria will apply:

- QTcF >500 msec OR uncorrected QT >600 msec
- Change from baseline of QTcF >60 msec

For participants with underlying bundle branch block, follow the discontinuation criteria listed below:

Baseline QTcF with Bundle Branch Block	Discontinuation QTcF with Bundle Branch Block
<450 msec	>500 msec
450 – 480 msec	≥530 msec

The QTcF value from the 12-lead ECG central over-read at randomisation Visit 2 should be used as baseline QTcF value for any changes from baseline calculations during the study. After randomisation 12-lead ECG central over-read values should be used to assess QTc stopping criteria, with the exception of Visit 10 (Week 26) where 12-lead ECG machine read values should be used.

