8.3.3. Electrocardiograms (ECGs)

- Twelve-lead ECGs will be obtained at the time points specified in the SoA (see Section 1.3) using an ECG machine, provided by GSK via a designated central laboratory, that automatically calculates the heart rate and measures PR, QRS, QT, and QTc intervals.
- The QTcF formula must be used for *each* individual participant to determine eligibility. This formula may not be changed or substituted once the participant has been enrolled. Refer to Section 7.1.2 for the QTcF formula.
- If an ECG demonstrates a prolonged QT interval, obtain two more ECGs over a brief period, and then use the averaged QTcF values of the three ECGs to determine whether the participant should be screened/ randomised/ discontinued from the study intervention (but not from the study). Refer to Section 5.2 and Section 5.3.2 for exclusion/randomisation exclusion criteria related to ECG assessment and Section 7.1.2 for QTc withdrawal criteria and additional QTc readings that may be necessary.
- ECG measurements will be made after the participant has rested in the supine position for 5 minutes. The ECG should be obtained after the vital signs assessments but before lung function testing followed by other study procedures. Collection shortly after a meal or during sleep should be avoided since QT prolongation can occur at these times.
- Paper ECG traces will be recorded at a standard paper speed of 25 mm/sec and gain of 10 mm/mV, with a lead II rhythm strip. There will be electronic capture and storage of the data by a validated method.
- Paper ECG traces are required to be maintained at the site with other source documents.

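### SAP 4.6.3.3: the QTcF-change rows overlap at exactly 60 msec and the uncorrected-QT rows at exactly 600 msec, where the protocol's limits are strict

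*SAP*

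**What the plan says.** SAP Section 4.6.3.3 (ECG) plans two categorical displays that matter here. Maximum QTcF changes from baseline are grouped as "increase of ≤ 30 , increase of 31 to 60 and increase of ≥ 60" (msec). Maximum uncorrected QT is grouped as "Decrease, no change or increase to ≤ 600 and increase to ≥ 600".

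Protocol Section 7.1.2 states its limits with strict inequalities: "QTcF >500 msec OR uncorrected QT >600 msec" and "Change from baseline of QTcF >60 msec".

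QTc prolongation is an adverse event of special interest (AESI). SAP Section 4.6.2.1 leaves it out of the AESI-specific tables and points to the ECG section: "AESI of QTc prolongation will be summarised as detailed in Section 4.6.3.3 ECG". Protocol Section 8.3.3 asks for two further ECGs after a prolonged QT, and then to "use the averaged QTcF values of the three ECGs" when deciding on screening, randomisation or discontinuation of study intervention.

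**The concern.** Rows that count each participant once, by a maximum value, should be mutually exclusive and should cover every possible value. These do not. Followed literally, a participant at exactly 60 or exactly 600 msec is counted in two rows, so the rows can add to more than the number of participants. The same participant also appears in the highest row while not exceeding the protocol's limit.

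The categories belong to the section assigned to this AESI, and high QT values are usually rare. Where a row holds few participants, one wrongly placed person is visible in the comparison of arms.

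**Working it through.** No sample size, power or alpha figure is involved. The check takes the printed categories as inequalities, asks how many rows each value falls into, and sets the result against the protocol's limits.

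**Inputs**
- QTcF change rows (SAP 4.6.3.3): x ≤ 30; 31 ≤ x ≤ 60; x ≥ 60.
- Uncorrected QT rows (SAP 4.6.3.3): x ≤ 600; x ≥ 600.
- Maximum QTcF bands (SAP 4.6.3.3): cut-points at 450, 480, 500 and 530, each open below and closed above, the last strictly above 530.
- Protocol limits (7.1.2): QTcF change > 60; QT > 600; QTcF > 500.
- Planned arm sizes (Protocol 9.2): 250 active, 125 placebo.

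**Check.** Values were taken in steps of 1 msec, and in steps of 1/3 msec to represent the mean of three whole-msec readings (30 + 1/3 = 30.33; 30 + 2/3 = 30.67).

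| Value (msec) | SAP row(s) | Exceeds protocol limit? |
|---|---|---|
| QTcF change 30 | ≤30 | no |
| QTcF change 30.33 or 30.67 | none | no |
| QTcF change 31 | 31 to 60 | no |
| QTcF change 60 | 31 to 60 **and** ≥60 | no |
| QTcF change above 60 | ≥60 only | yes |
| QT below 600 | ≤600 only | no |
| QT 600 | ≤600 **and** ≥600 | no |
| QT above 600 | ≥600 only | yes |

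**Results**
1. On the whole-msec grid there is one overlap in each display, at 60 and at 600, and no gap.
2. On the 1/3-msec grid the same two overlaps appear, and 30.33 and 30.67 fall in no QTcF-change row.
3. The maximum-QTcF bands have no overlap and no gap on either grid, and their cut at 500 agrees with the protocol's strict limit.
4. SAP top row and protocol limit disagree only at exactly 60 and exactly 600. No value beyond a limit is lost or placed in a lower row.
5. The lowest QTcF-change row does not say that decreases and no change belong to it, although the two neighbouring displays name them.
6. One participant is 1/250 = 0.4% of the planned active arm and 1/125 = 0.8% of the planned placebo arm.

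With rows ≤30, >30 to ≤60 and >60 for QTcF change, and ≤600 and >600 for QT, every value on both grids falls in exactly one row.

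**The case against.** A reader might go further and infer that this is the only planned display of QTc prolongation and that it miscounts outliers. The documents do not support that. Section 4.6.3.3 also plans QTcF change by visit, ECG findings by visit, the non-overlapping maximum-QTcF bands, and a listing of participants selected on the protocol's own QT criteria. Reported QTc events would also appear in the general adverse event tables (SAP 4.6.2). Every value above 60 or 600 msec is in the top row and in no other.

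A reader might also expect the top rows to reconcile with the stopping-criteria listing. The SAP does not promise this, and corrected signs would not guarantee it: Protocol 7.1.2 uses machine-read values at Visit 10, central over-read values at other visits after randomisation, and separate limits for bundle branch block.

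The gap between 30 and 31 is conditional. The averaging in Protocol 8.3.3 serves eligibility and discontinuation decisions. Neither document says that the average feeds this table, or that it is left unrounded. The row "increase of 31 to 60 and increase of ≥ 60" starts from can be read as a whole-msec convention, under which there is no gap. Display conventions are deferred to the Output and Programming Specification (SAP Section 1), which is not available here.

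Lastly, the inequality text in this section is partly garbled by conversion from PDF, so a lost strict sign is conceivable. The same section prints a strict sign at 530 and gives properly separated bands, which makes a general loss of strict signs unlikely.

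These objections limit the point's reach. They do not remove the overlaps at 60 and 600.

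**Conclusion.** As printed, the rows overlap at exactly 60 msec for QTcF change and at exactly 600 msec for uncorrected QT. At those two values the top row also differs from the protocol's strict limits. This is a minor counting error in a descriptive safety table. It affects only participants whose maximum is exactly on a boundary, plus those between 30 and 31 msec if fractional averages are used. Few are likely; the documents give no basis for a frequency.

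No test depends on these rows: SAP 4.6.2.1 leaves QTc prolongation out of the relative-risk and risk-difference summary. Discontinuation decisions follow Protocol 7.1.2, not this table.

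The conclusion assumes that the inequality signs in the available text are those of the SAP. The gap between 30 and 31 further assumes that unrounded values reach the table.

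**What to change.** In SAP Section 4.6.3.3 and the table shells, make the rows exclusive and exhaustive, with cut-points consistent with the protocol's own limits:
- Maximum QTcF change from baseline: ≤30 msec (including decreases and no change); >30 to ≤60 msec; >60 msec.
- Maximum uncorrected QT: ≤600 msec; >600 msec.

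Writing the middle row as >30 to ≤60 closes the possible gap whatever rounding is used. It would still help to state, in the SAP or the programming specification, whether averaged repeat ECGs enter these displays.

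The cost is a few characters of text. No new data or analysis is needed, and the stopping criteria in Protocol 7.1.2 stay as they are.

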4.6.3.4. Complement

Complement (C3 and C4) will be summarised by parameter and visit and presented as a table. The summary table will include baseline concentration, concentrations at each visit and ratio to baseline at each visit. Summary statistics to be presented are n, geometric mean, SD of logs, median, minimum and maximum.

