8.3.4. Clinical Safety Laboratory Assessments

- See Appendix 2 for the list of clinical laboratory tests to be performed and refer to the SoA (Section 1.3) for the timing and frequency.
- The investigator must review the laboratory report, document this review, and record any clinically significant changes occurring during the study as an AE. The laboratory reports must be filed with the source documents.
- Abnormal laboratory findings associated with the underlying disease are not considered clinically significant, unless judged by the investigator to be more severe than expected for the participant's condition.
- All laboratory tests with values considered clinically significantly abnormal during participation in the study until the Exit Visit (or Follow-up visit/call if applicable) should be repeated until the values return to normal or baseline or are no longer considered significantly abnormal by the investigator or Medical Monitor. If clinically significant values do not return to normal/baseline within a period of time judged reasonable by the investigator, the aetiology should be identified, and the Sponsor notified.

- If laboratory values from non-protocol specified laboratory tests performed at the institution's local laboratory require a change in participant management or are considered clinically significant by the investigator (e.g., SAE or AE), then the results must be recorded.
- All protocol-required laboratory assessments, as defined in Section 10.2, must be conducted in accordance with the laboratory manual and the SoA (Section 1.3).
- To maintain the treatment blind, the site and the central study team will not be sent information on haematology differential (absolute and % values of eosinophils, lymphocytes, basophils, neutrophils, and monocytes) from any visits post-randomisation.

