10.3.1. Definition of AE

AE Definition

 An AE is any untoward medical occurrence in a clinical study participant, temporally associated with the use of a study intervention, whether or not considered related to the study intervention. 
NOTE: An AE can therefore be any unfavourable and unintended sign (including an abnormal laboratory finding), symptom, or disease (new or exacerbated) temporally associated with the use of a study intervention.

Events Meeting the AE Definition

 Any abnormal laboratory test results (haematology, clinical chemistry, or urinalysis) or other safety assessments (e.g., ECG, radiological scans, vital signs measurements), including those that worsen from baseline, considered clinically significant in the medical and scientific judgment of the investigator (i.e., not related to progression of underlying disease). Exacerbation of a chronic or intermittent pre-existing condition including either an increase in frequency and/or intensity of the condition. New conditions detected or diagnosed after study intervention administration even though it may have been present before the start of the study. Signs, symptoms, or the clinical sequelae of a suspected intervention- intervention interaction. Signs, symptoms, or the clinical sequelae of a suspected overdose of either study intervention or a concomitant medication. Overdose per se will not be reported as an AE/SAE unless it is an intentional overdose taken with possible suicidal/self-harming intent. Such overdoses should be reported regardless of sequelae. "Lack of efficacy" or "failure of expected pharmacological action" per se will not be reported as an AE or SAE. Such instances will be captured in the efficacy assessments. However, the signs, symptoms, and/or clinical sequelae resulting from lack of efficacy will be reported as AE or SAE if they fulfil the definition of an AE or SAE.

Events NOT Meeting the AE Definition

- Any clinically significant abnormal laboratory findings or other abnormal safety assessments which are associated with the underlying disease, unless judged by the investigator to be more severe than expected for the participant's condition.
- The disease/disorder being studied or expected progression, signs, or symptoms of the disease/disorder being studied, unless more severe than expected for the participant's condition.

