4.11.1. IDMC Safety Review

IDMC will periodically review unblinded safety data from the three Phase III studies in the severe asthma program: 206713, 213744 (this study) and 206785, in accordance with the IDMC Charter. IDMC will also review safety data from study 212895, an open-label extension study including participants who were previously enrolled in study 206713 or 213744 when sufficient data is collected.

The IDMC will review all safety data, including AEs and serious adverse events (SAEs) and adverse events of special interest (AESI), laboratory parameters, including

haematological and clinical chemistry parameters and ECG assessments from the three studies for identification of any potential safety signals. The safety data analyses for the IDMC reviews will be performed by an independent Statistical Data Analysis Centre (SDAC).

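### The planned C3/C4 table (SAP 4.6.3.4) can hint at a heavier lower tail on active but cannot count participants per arm whose complement was ever low or falling after baseline

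*SAP*

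**What the plan says.** SAP 4.6.3.4 gives complement its own short section: "Complement (C3 and C4) will be summarised by parameter and visit and presented as a table". The table covers the baseline concentration, the concentration at each visit and the ratio to baseline at each visit. The statistics form a closed list: "Summary statistics to be presented are n, geometric mean, SD of logs, median, minimum and maximum". The section plans no lowest value per participant, no count below a limit, no shift from baseline and no listing. It does not name treatment group, although display by arm is probably intended.

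The schedule of activities (protocol 1.3) takes C3 and C4 at Weeks 0, 12, 26, 40 and 52 and at the withdrawal visit. Protocol 7.5 includes a decrease in C3/C4 among the laboratory abnormalities potentially suggestive of vasculitis. Type III hypersensitivity is an adverse event of special interest (protocol 8.4.7, SAP 4.6.2.1).

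The general laboratory section, SAP 4.6.3.1, reads: "Summaries of laboratory data including chemistry and haematology parameters, and liver chemistry test data will be based on GSK Core Data Standards". Complement is not named there, and it is not in the protocol's safety laboratory table (Appendix 2, Table 5). For QTcF, the SAP does plan per-participant worst values: "Individual maximum QTc(F) values will also be summarised to show the number of subjects with maximum values (msec) post-baseline relative to baseline" (4.6.3.3). SAP 4.7 likewise summarises each participant's highest post-baseline antibody result.

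**The concern.** The safety question that complement serves concerns individuals: did C3 or C4 fall in some participants, and in a larger share of them on active? A table built from each visit's distribution does not answer that directly. The minimum describes one person. The geometric mean and median barely move when a few percent are affected. The SD of logs responds, but it does not convert into a number of people. Rows for separate visits also cannot be joined into a per-participant result.

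At stake is what the scheduled samples add beyond reported events, namely whether falls that no investigator judged significant were more frequent on active. Detection of reported vasculitis does not depend on this table.

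**Working it through.** The documents give no figure on this point to reproduce, so the check asks what the listed statistics can and cannot determine.

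**Inputs.** Planned arm sizes are 250 active and 125 placebo (SAP 5). There are four scheduled post-baseline visits, Weeks 12, 26, 40 and 52 (protocol 1.3). The documents give no variability for C3/C4, so the SD s of the log ratio to baseline in unaffected participants is an assumption, taken as 0.10, 0.15 and 0.20. The size of a fall, half of baseline, is also an illustration.

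**1. Across visits (no SD assumption).** Let k(v) be the number low at visit v. The number ever low lies between the largest k(v) and the sum of the k(v). With k = 5 at each of 4 visits:
- same five people each time: 5/250 = 2.0%
- different people each time: 4 × 5 = 20, and 20/250 = 8.0%

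Each visit's set of values is the same in both cases, so every planned statistic is the same. A constructed example confirms it. Five values from 0.50 to 0.70 of baseline and 245 values above 0.75 give, at every visit in both cases, geometric mean ratio 0.983, SD of logs 0.148, median 0.991, minimum 0.50 and maximum 1.538. The number ever below 0.75 of baseline is 5 in one case and 20 in the other.

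**2. At one visit, between arms.** Suppose k of n participants have C3 at half of baseline and the rest are centred on no change. Then:
- geometric mean ratio = 0.5^(k/n)
- SD of logs = sqrt{[(n − k − 1)s² + (k(n − k)/n)(ln 2)²]/(n − 1)}

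| | Placebo, 1/125 | Active, 10/250 |
|---|---|---|
| Proportion halved | 0.8% | 4.0% |
| Geometric mean ratio | 0.994 | 0.973 |
| Minimum ratio | 0.50 | 0.50 |
| SD of logs, s = 0.10 | 0.117 | 0.168 |
| SD of logs, s = 0.15 | 0.162 | 0.200 |
| SD of logs, s = 0.20 | 0.209 | 0.239 |

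So the planned statistics do differ between arms. The SD of logs is visibly larger on active, less clearly so as s rises. A reader would see a wider spread, but not that 10 people rather than 1 were affected, nor that the proportion was five times as large.

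**3. What a count would show.** The difference is 4.0% − 0.8% = 3.2 percentage points. The Wilson limits are 2.19% to 7.21% and 0.14% to 4.39%. Newcombe's 95% interval is then
- lower: 3.2 − sqrt(1.81² + 3.59²) = −0.8
- upper: 3.2 + sqrt(3.21² + 0.66²) = 6.5

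The count is descriptive and would not by itself settle a difference between arms.

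**4. What the minimum does tell.** If nobody is affected, the chance of a minimum ratio of 0.50 or lower among 250 is 1 − [1 − Φ(ln 0.5/s)]^250. That is below 0.001 at s = 0.10 and 0.15, and 0.064 at s = 0.20. The minimum is therefore a fair flag that at least one participant fell this far, but it does not say how many.

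**The case against.** The strongest reply is that little is left uncovered.

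- **Adverse events.** Investigators must "record any clinically significant changes occurring during the study as an AE" (protocol 8.3.4). C3/C4 are not among the results withheld from sites.
- **Events of special interest.** On the vasculitis event itself: "Vasculitis events and local injection site reactions are also collected via targeted eCRF within the study" (SAP 4.6.2.1), with relative risk and risk difference between arms.
- **Monitoring.** The committee sees unblinded data: "The IDMC will review all safety data, including AEs and serious adverse events (SAEs) and adverse events of special interest (AESI), laboratory parameters" (SAP 4.11.1).
- **Room in the plan.** SAP 4.6 foresees frequency tables for laboratory data where appropriate, protocol 9.4.5 adds listings, and the panels in SAP 4.6.3.1 are given as inclusions, not as a full list. Display detail is left to the OPS.
- **QTcF is an imperfect comparison.** It has protocol stopping thresholds from which categories follow. Complement has no threshold, and continuous summaries are a defensible default for such a marker.

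Most of this stands, and it sets the size of the point. It does not remove it. Recording as an adverse event turns on whether a change is "considered clinically significant in the medical and scientific judgment of the investigator" (protocol 10.3.1), so falls not judged significant are counted nowhere in the SAP text. Event tables cover reported events. Committee review is oversight and does not specify an analysis for the study report. None of the general laboratory provisions names complement, and the OPS cannot be checked here. The antibody summary shows that per-participant worst results are planned even where no stopping threshold exists.

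**Conclusion.** The point holds as a cheap improvement of minor severity. The by-visit statistics in SAP 4.6.3.4 can suggest a heavier lower tail on active, but they cannot give the number or percentage of participants per arm with low or falling C3/C4 at any time after baseline. The gap is limited to falls that nobody reported.

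The across-visit ambiguity (5 to 20 of 250) follows from the structure of the table. The between-arm figures rest on assumed SDs and an illustrative halving.

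A reader might infer that an imbalance in complement would be invisible, or that vasculitis could go undetected. The documents do not support either. In the worked example the SD of logs and the geometric mean do separate the arms, and reported events follow their own route to collection and comparison. Nor can one conclude that no count is planned anywhere, because the OPS may contain one.

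**What to change.** In SAP 4.6.3.4 add, by treatment arm and over scheduled post-baseline visits:

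1. Each participant's lowest C3 and C4 value and lowest ratio to baseline, summarised, with the number and percentage of participants in descriptive ratio categories fixed before unblinding. Below 0.75 and at or below 0.50 of baseline would serve as examples. The documents give no threshold, so the sponsor chooses.
2. The number and percentage of participants below the testing laboratory's lower limit of normal, with shifts from normal at baseline to low.

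Both parts are needed: a participant whose C3 halves may stay within the reference range, so a count against the lower limit alone would not recover the falls illustrated above.

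Protocol 7.5 allows unscheduled C3/C4 samples at the time of a suspected event. These are event-driven and should enter only a supportive repeat. Their handling rule and any listing can stay in the OPS. If the OPS already holds such a display, moving its definition into the SAP is enough.

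The cost is one extra descriptive table from data already collected, the choice of cut-offs, and the reference limits from the laboratory. No sample, endpoint, test or stopping rule changes.
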